Military Institute of Aviation Medicine

Research Protocol

**Clinical evaluation of a fibre-optic sensor system for monitoring
respiration activity and heart work during MRI examinations**

Project PBS3/B9/41/2015

January 3, 2017

Table of Contents

Project summary	3
General information	4
Protocol Title	4
Short title	4
Acronym	4
Sponsor	4
Primary Investigator (PI)	4
Other medical and/or technical institutions involved in the research	4
Rationale & background information	5
Study goals and objectives	6
Study Design	6
Methodology	7
Fibre-optic sensor system	7
MRI scanner	8
STAI	8
Safety Considerations	8
Follow-Up	8
Data Management	9
Statistical Analysis Plan	9
Quality Assurance	9
Expected Outcomes of the Study	9
Dissemination of Results and Publication Policy	10
Duration of the Project	10
Problems Anticipated	10
Project Management	10
Ethics	10
Informed Consent Forms	11
Literature	11
Budget	13
Other support for the Project	13
Collaboration with other scientists or research institutions	13
Links to other projects	13
Curriculum Vitae of investigators	13
PI's Curriculum Vitae	13
Other investigators	15
Research activities of the PI	15
Financing and Insurance	15
Appendix A	16
Appendix B	17
Appendix C	18

Project summary

The main purpose of the project is to determine the possibility of assessing the level of anxiety by means of the respiration curve and/or ballistocardiographic (BCG) signal acquired from MRI patients using a fibre-optic sensor system. In many patients, the MRI examination causes enormous stress due to limited space in the scanner, isolation during the examination and high noise levels. Usually, anxiety or stress triggers an increase in respiration rate (RR), leading to hyperventilation in extreme cases. There are also frequent cases of disturbances in heart rate (HR). Thus, the symptoms of claustrophobia can be detected by monitoring respiration activity and heart work.

The fibre-optic sensor system consists of a sensor mat, an interrogator and a personal computer (PC), and records respiratory and BCG signals in patients during MRI. The metal-free sensor mat is placed under the patient's back, does not pose a threat to the patient and has no influence over the quality of imaging. The interrogation module detects the optical signal including vital signs, and the PC with software developed for signal processing and visualisation enable the MRI operator to monitor patient's RR and HR.

Up to 200 MRI patients in different age, weight and gender groups will be participated in the study. They will be asked to complete the State Trait Anxiety Inventory (STAI) questionnaire in order to estimate anxiety level before and after the MRI scanning. Relations between the STAI X-1 scores and the mean RR and/or HR values recorded at the beginning and the end of the MRI scanning will be analysed using descriptive statistic methods. Finally, the values of the physiological parameters, which may indicate a dangerous level of anxiety will be determined. Positive results of the clinical evaluation will predestine the fibre-optic sensor system to be implemented in routine MRI procedures.

General information

Protocol Title

Clinical evaluation of a fibre-optic sensor system for monitoring respiration activity and heart work during MRI examinations

Short title

Evaluation of an MRI-compatible vital signs sensor system

Acronym

OPTO-MRI

Sponsor

Military Institute of Aviation Medicine (MIAM)
[name]
[name]
Poland

Primary Investigator (PI)

[name], D.Sc., Ph. D.
[name]
[name]
Poland
[contact]
email: [contact]

Other medical and/or technical institutions involved in the research

No other co-operators

Rationale & background information

Recently, magnetic resonance imaging (MRI) has become one of the most common and reliable diagnostic methods in medicine. The results of the still improving imaging performances, new functionalities, and more affordable prices represent a pronounced trend toward equipping hospitals and clinics with MRI scanners [1]. The rapid development of this technology has created the need to construct devices capable of monitoring vital signs of at-risk patients during MRI examinations. The risk group in the context of MRI includes neonatal, paediatric, disabled, anesthetised, and insensible patients [2]. The monitoring of life functions is also recommended for persons with implanted pacemakers, patients developing reactions to contrast media, and persons with mental disorders who may not be able to communicate with the system operator or to use the alarm button. However, efforts are being made to monitor at least some basic physiological parameters such as respiration and heart activity [3] during each MRI examination, regardless of the patient category.

Although MRI is a noninvasive method of investigation and does not expose patients to ionizing radiation, it has some psychological effects on patients. Some researchers [4],[5] have already demonstrated that 5 to 10% of patients undergoing MRI examinations experience severe claustrophobia or panic attacks during the scanning process, whereas 30% report milder distress and fear. Such increased stress stimuli and arousal may in turn lead to a phenomenon known as hyperventilation, which is increased ventilation of the lungs and significant acceleration and deepening of the breath, often resulting in fainting.

Hyperventilation has numerous theoretical and empirical links to anxiety, panic, and fear episodes [6],[7]. This phenomenon was investigated in order to understand psychological and physiological mechanisms connected with hyperventilation that cause and maintain anxiety. On the other hand, attempts were also made to find a link between hyperventilation and the therapies used to treat different types of anxiety disorders. Some results [8] support the idea of higher variability and irregularity in the respiratory patterns of subjects with panic disorder. Other clinical studies [9] have shown that controlling and normalising the subject's breathing activity helps to reduce both anxiety and panic symptoms. On the basis of this assumption, different training and therapeutic programs [10] have been created and carried out with the aim of teaching patients to breathe in a specific way to avoid or reverse hyperventilation, e.g., capnometry-assisted respiratory training (CART) [11]. Furthermore, attempts have also been made to study the relationship between different anxiety disorders and cardiological parameters. The literature [12] reveals an increased heart rate (HR) level in a group of people suffering from panic, anxiety disorders, and hyperventilation symptoms.

In light of recent scientific reports, it seems obvious that MRI examinations can be a source of extreme stress and cause anxiety and panic symptoms in some patients. People who experience anxiety, fear, or hyperventilation during an MRI scan may either discontinue the procedure altogether or refuse to undergo MRI surveys in the future. In practice, it is very important to identify those who are likely to panic and experience anxiety-related symptoms in the MRI unit as early as possible, because only early detection ensures that appropriate actions can be taken to avoid psychological discomfort for the patient undergoing the scan and unnecessary use of the machine, as well as staff involvement in the entire procedure. Real-time monitoring of certain life functions in the patient, such as respiration rate (RR) and HR, can be helpful in controlling the arousal and anxiety level associated with the MRI examination itself and predicting the probability of a panic attack.

Conventional monitoring equipment is not designed to work in the harsh MRI environment, distinguished by a magnetic induction of 1.5 T, 3.0 T, or even higher values and with radio frequency (RF) impulses of considerable electromagnetic (EM) field intensity [13]. The presence of metal or electronic components under such conditions can cause burns on the patient's skin and alter the EM field distribution and, thus, degrade the quality of imaging. Additionally, the signal transmitted using electrical conductive wires is vulnerable to the effects of a strong EM field, which complements the list of drawbacks of typical electronic measuring devices. On the other hand, optical sensors are fully penetrable in terms of the EM radiation applied in MRI, causing no interference. They are free from metal parts and function via optical fibres, resulting in their immunity to EM fields.

Study goals and objectives

The main objectives include:

1. Testing the sensor system with participation of MRI patients, where the result measures relate both to feasibility and health outcomes.
2. Verifying the signal quality, detecting RR and HR, and checking long-term measurement capabilities of the sensor system.
3. Analysing changes in RR and HR in the context of the system ability to detect a high level of stress, hyperventilation and other symptoms of claustrophobia in MRI patients.

Study Design

The acquisition of physiological signals relies on placing the sensor mat under the patient's back during standard MRI procedures. Before and after the MRI scanning, the patient gets to complete the State Trait Anxiety Inventory (STAI) questionnaire. The part of the body that is being scanned and the time of the MRI examination are not relevant. Although an average MRI scanning lasts from 20 to 40 minutes, we assume that the study will be no longer than 1 hour as the administration of contrast media may prolong the survey. Up to 200 MRI patients of different age, weight and sex will be involved in the study. Exclusion criteria from the study are the same as exclusion criteria from MRI procedures. The sensor mat does not cause health changes in patients and the study is of observational type. The analysis will concern changes in RR and/or HR during MRI, with particular emphasis on the beginning and the end of the examination, i.e., 1- or 2-minute parts of the whole recording, as it shown in Fig. 1. The mean RR and/or HR values recorded at the beginning and the end of the MRI scanning will be referred to the STAI X-1 scores gathered before and after the MRI scanning, respectively. The research scheme includes also the collection of the STAI X-2 subscale before the MRI scanning.

[figure not shown]

Fig. 1. General scheme of the study.

Methodology

Fibre-optic sensor system

The sensor system consists of a sensor mat, an interrogation module and a laptop personal computer (PC). As shown in Fig. 2, the sensor mat includes a spring-board that converts body movements including lung- and heart-induced motions into strain, and a single fibre Bragg grating (FBG) or an FBG matrix bonded to the board measures this strain. The instantaneous spectral position of the FBG reflection peak can be calibrated in terms of the respiration and heart activity readings. Thus, the sensor also acquires ballistocardiographic (BCG) signals, and to operate effectively, the mat has to be placed between the back of the patient (as close to the heart as possible) and the mattress of the MRI track table.

[figure not shown]

Fig. 2. Sensor mat based on a (a) single FBG and (b) FBG matrix.

A schematic of the research setup is shown in Fig. 3. The sensor mat is placed in the MRI chamber underneath the chest area of the patient to ensure proximity to the heart and lungs. A few meters optical fibre is threaded through a wall opening and connected via a fibre-optic for angled physical contact (FC/APC) -type connector to an FBG interrogation module in the operation room. To interrogate the sensor mat, a commercially available DL-BP1-1501A broadband light source by *DenseLight Semiconductors* [14] with I-MON 256/512 USB monitor by *Ibsen Photonics A/S* [15], or sm130-700 integrated unit by *Micron Optics* [16] will be used. The data from the interrogation module is sent via an USB or Ethernet interface

to the laptop PC with software developed for signal visualisation, data archiving as well as automatic determination of RR and HR.

[figure not shown]

Fig. 3. Research setup.

MRI scanner

Achieva 1.5T by *Philips* [17] or Discovery MR750w 3.0T by *General Electric* [18] MRI scanners will be used in the study.

STAI

In order to measure anxiety in patients undergoing MRI procedures, the Polish version of the STAI by Spielberger et al. [19] was used. The inventory is designed to measure the level of anxiety as a current state in response to a given situation (the X-1 subscale) as well as a relatively stable personal trait (the X-2 subscale). Evaluation of anxiety level in patients will be conducted according to a repeated measurement protocol. The subjects will complete the STAI X-1 subscale twice, i.e., just before entering the MRI scanner and immediately after leaving the scanner. The STAI X-2 subscale will be completed before the MRI scanning. As a result, the level of experienced anxiety before and after the MRI scanning, as well as the level of anxiety as a constant personality trait in patients, will be obtained.

Safety Considerations

The presence of the sensor mat during the MRI examination does not pose a threat to the patient. Because the sensor mat is free from metal elements, it is fully penetrable by the EM radiation used in MRI and causes no interference. We have previously showed that the fibre-optic sensor is transparent to the MRI system and does not introduce any artefacts into the spin echo (SE) T1 weighted and T2 weighted or to the gradient echo (GE) T2 weighted imaging sequences [20],[21].

Follow-Up

No recommendations other than for standard MRI procedures.

Data Management

MIAM is both a research institute and medical centre, where data management and information security are provided in accordance with the ISO IEC 27001 standard. A copy of the certificate is included as **Appendix A**.

Statistical Analysis Plan

Descriptive statistic methods will be used to evaluate the state anxiety and RR and/or HR indicators, as well as to assess the difference between the first and second anxiety measurement. A correlation analysis with the Pearson product-moment correlation coefficient will be performed to check if the initial RR and/or HR level is related to state anxiety measured right before the MRI study.

Since we hypothesise about the individual variability of the change in the RR and/or HR levels during an MRI session, a growth mixture model analysis [22] will be performed to statistically differentiate the subject groups according to the trends in repeated measures of RR and/or HR. After that, the analysis will be performed with the use of the Student's t-test to check whether the so-identified groups differ on the magnitude of change in the state anxiety observed during the study. An Alpha level of 0.05 will be used in all of the statistical tests.

The analysis will be performed using R statistical software version 3.4.0 [23]. The Growth mixture model analysis will be performed using the lcmm package version 1.7.7 [24]. The power analysis will be performed with the pwr package version 1.2-1 [25]. Plots will be created using the ggplot2 package version 2.2.1 [26].

Quality Assurance

MIAM has a quality management certificate based on the ISO 9001:2008 and AQAP 2120:2009 requirements. Copies of the certificates are included as **Appendix B**.

Expected Outcomes of the Study

Correlations between the STAI X-1 scores collected before and after the MRI scanning and the mean RR values recorded at the beginning and the end of the MRI scanning, respectively, are expected. Similarly, correlations between the STAI X-1 scores and the HR indicators should also be noticeable. We also expect the STAI X-2 scores will be useful in estimating the risk of anxiety symptoms during MRI.

At least two manuscripts, one containing the results of the STAI scores in relation to RR, and the other containing the results of the STAI and HR analysis, will be submitted for publication.

Dissemination of Results and Publication Policy

The results will be first reported to the National Centre of Research and Development (NCRD), Poland, in the form of mile stone reports.

The publications will be prepared under the leadership of the PI. The PI decides on the author lists. Only persons who gave the conception of the sensor system, designed and constructed the sensor mat, designed the experimental protocol, coordinated the study, processed data for analysis, analysed and verified data, and interpreted the results, can be included on the author lists. The person who contributes the most to the preparation of the manuscript will be its first author. If the PI is not the author of the largest contribution, he will be acknowledged as the last author of the article.

All authors will review the manuscripts and accept their final version.

Duration of the Project

Duration of the project is July 2015 - September 2018.

Realisation of the research scenarios is scheduled for January 2017 - September 2018.

Problems Anticipated

Two main types of problems are anticipated: (1) patients' anxiety reactions and (2) hardware failures. In the first case, we will follow typical MRI procedures, including calming the patient and restoring or abandoning the examination. In the event of the fibre-optic sensor system failure, the patient monitoring and data acquisition will take place shortly after the fault has been removed.

Project Management

The project is managed in accordance with the PRINCE2 methodology. The PI manages the investigators including the project coordinator and the study coordinator. The PI shall consult and report the results of the project to the Steering Committee.

Ethics

The fibre-optic sensor system does not pose any threats to the patient. Disturbing symptoms may result from the patient's potential claustrophobic tendencies. In such cases, the standard MRI procedures should be followed.

Potential subjects will be informed on the study at least 2 weeks before the planned study. Those who are initially interested in the study participation will receive a copy of the research protocol for acquainting. They should decide at least 3 days before the beginning of the planned study and inform the study coordinator. Just before the study, the subjects will

receive two copies of the informed consent form to acquaint and sign. One of the signed copies is for the subject whereas the other is for the sponsor.

Informed Consent Forms

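### The Project summary promises RR/HR values that may indicate dangerous anxiety, but the SAP's analyses test only group-level association and do not yield such values or their detection accuracy

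*Combined protocol and SAP*

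**What the plan says.** The promise is in the Project summary. Relations between X-1 scores and mean RR and/or HR at the start and end of the scan "will be analysed using descriptive statistic methods", and finally "the values of the physiological parameters, which may indicate a dangerous level of anxiety will be determined". The next sentence adds: "Positive results of the clinical evaluation will predestine the fibre-optic sensor system to be implemented in routine MRI procedures".

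In Study goals and objectives, the third objective reads in part: "Analysing changes in RR and HR in the context of the system ability to detect a high level of stress, hyperventilation and other symptoms".

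Study Design sets the pairing: mean RR and/or HR at the start and end of the scan "will be referred to the STAI X-1 scores gathered before and after the MRI scanning, respectively". The STAI section says X-1 is completed "just before entering the MRI scanner and immediately after leaving the scanner".

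Besides descriptive statistics, the Statistical Analysis Plan section has two inferential steps. A Pearson correlation is to "check if the initial RR and/or HR level is related to state anxiety measured right before the MRI study". A growth mixture model then sorts patients by their RR/HR trends, and a t-test is to "check whether the so-identified groups differ on the magnitude of change in the state anxiety observed during the study". Alpha is 0.05 throughout. Enrolment is up to 200 patients.

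**The concern.** Determining a value that indicates dangerous anxiety needs three things: a definition of the patients to be detected, a rule that turns the RR/HR data into a value, and an estimate of how often that value is right and wrong in individual patients. The documents supply none of them. X-1 is a named anxiety measure, but no score on it is called high or dangerous.

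A team that follows the SAP exactly can therefore finish with a significant correlation, or a significant difference between trend classes, and still have no basis for the sentence in the summary. If a cut-off were then added after the data were seen, and chosen and judged on the same patients, its accuracy would look better than it is.

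**Working it through.** **1. The promise against the planned analyses.** The plan states no threshold, accuracy target, expected correlation or power, so there is no figure to reproduce. Each planned step can be set against the promised values:

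- Descriptive statistics give distributions of X-1, RR and HR, and typical RR/HR values per trend class. They give no error rates.
- The Pearson correlation gives the strength of a linear relation between initial RR/HR and pre-scan X-1. It gives no cut-off and no error rates.
- The growth mixture model groups patients by RR/HR trajectory. Anxiety status plays no part in forming the classes.
- The t-test compares mean X-1 change between those classes. It says nothing about classifying individual patients.

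**2. Does a significant correlation settle detection? (illustration)** Input from the documents: N = 200, which is a ceiling, and alpha 0.05. Assumptions: two-sided test, bivariate normal data, and cases defined as the top 10% of X-1 (5% and 30% as a range). These shares are borrowed from the Rationale section, where they describe reactions during the scan, not high X-1 before or after it. The documents give no expected r.

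- Smallest significant |r| = t/√(198 + t²), with t(0.975, 198) = 1.972: 1.972/√(198 + 3.889) = 0.139.
- At r = 0.30: t = 0.30 × √198/√(1 − 0.09) = 4.43, p = 0.000016.
- False alarms per 100 scans = 100 × (1 − case share) × (1 − specificity), with the cut-off set at 80% sensitivity. At r = 0.30 and a 10% case share, specificity is 0.410, so 100 × 0.90 × 0.590 = 53.1. The same 100 scans contain 10 cases, of which 8 are caught.

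| r | AUC (top 5% / 10% / 30%) | False alarms per 100 scans |
|---|---|---|
| 0.139 | 0.59 / 0.58 / 0.57 | 67 / 64 / 51 |
| 0.30 | 0.68 / 0.66 / 0.64 | 54 / 53 / 44 |
| 0.50 | 0.80 / 0.77 / 0.74 | 35 / 37 / 33 |

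**3. What a detection analysis on these data could support.** In the r = 0.30 scenario with 200 patients, expected cases are 200 × 0.05, 0.10 or 0.30 = 10, 20 or 60. Simulated trials (10,000) give a 95% sampling range for the AUC of 0.50–0.85, 0.53–0.78 or 0.56–0.72.

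A cut-off picked at the maximum Youden J (sensitivity + specificity − 1) and judged on the same patients was checked with 600 simulated trials of 200 bootstrap resamples each, repeating the selection in every resample. With the top 10% as cases, mean J was 0.335 apparent, 0.254 corrected and 0.211 true. The correction removes (0.335 − 0.254)/(0.335 − 0.211) = 65% of the optimism; it removes 62% and 70% at the 5% and 30% case shares.

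**The case against.** The strongest reply is that this is one hedged sentence in a summary. It says the values may indicate anxiety, and it is not repeated in the objectives, Study Design, SAP or Expected Outcomes. The stated main purpose is only to establish whether anxiety can be assessed from these signals, the study is observational, and the SAP does serve that purpose. Typical RR/HR values per trend class could also be read as the promised values. Much of this stands: the point is confined to that sentence. But the hedge qualifies what the values mean, not the commitment to produce them. Class averages are not tied to any level of anxiety, because the classes are not formed from anxiety, and the documents do not name that route.

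Three stronger readings are tempting and are not supported:

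- **That the third objective promises detection accuracy.** It commits only to analysing changes in the context of detection, and the growth model and t-test do analyse changes.
- **That routine use hinges on an RR/HR cut-off.** The sentence on implementation refers to positive results of the whole evaluation, which also covers feasibility, signal quality and RR/HR measurement. No section makes implementation depend on a cut-off.
- **That the plan will overstate accuracy.** That would follow only if a cut-off were chosen and judged on the same patients, which the documents neither plan nor exclude.

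It is also fair to say that the numerical illustration rests on an assumed r and borrowed case shares, and uses a single static RR/HR value. It shows that correlation is not discrimination; it does not forecast this study's result.

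**Conclusion.** The point holds in this limited form: one stated deliverable, the RR/HR values, has no analysis behind it. The planned association analyses are not called into question, and they remain adequate for the main purpose.

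The gap itself rests on the text alone and needs no assumption. Its practical size can only be illustrated: under the assumptions in the working, a correlation with p < 0.0001 goes with an AUC of about 0.66 and about 53 false alarms per 100 scans at 80% sensitivity. Across the assumed correlations (0.139 to 0.50) and case shares (5% to 30%), false alarms run from 33 to 67 per 100. This is a change that should be made, because a method can be specified at little cost from data already being collected.

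**What to change.** Add to the SAP a pre-specified exploratory detection analysis:

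1. High state anxiety is an X-1 threshold whose value and source the sponsor fixes before analysis.
2. One primary pairing is taken from Study Design, for example start-of-scan RR with pre-scan X-1.
3. The AUC is reported with a 95% CI.
4. Any candidate cut-off is reported with sensitivity, specificity and false alarms per 100 scans, corrected for optimism by a bootstrap that repeats the cut-off selection in every resample. It is labelled hypothesis-generating and in need of external validation.
5. The text states that the analysis addresses anxiety reported before and after the scan, not symptoms during it, and that a high X-1 score is not in itself shown to be dangerous.

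If few patients are expected above the threshold, reword the Project summary sentence to claim only association between RR/HR and state anxiety. The third objective need not change in either case.

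Cost: one SAP paragraph and a short analysis with no extra patients or visits, or a wording change alone. Downsides: intervals are wide if cases are few, the bootstrap removes only part of the optimism (62–70% in the check above), and the claim becomes more modest.

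### Anxiety-related RR/HR values are to be chosen in this one cohort and positive results are tied to routine use, with no validation, performance measure or confirmation step in between

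*Combined protocol and SAP*

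**What the plan says.** The Project summary sets the size of the study ("Up to 200 MRI patients in different age, weight and gender groups will be participated in the study") and its end product: "the values of the physiological parameters, which may indicate a dangerous level of anxiety will be determined". The sentence after that reads: "Positive results of the clinical evaluation will predestine the fibre-optic sensor system to be implemented in routine MRI procedures". No other data source for the values is named.

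Under Study goals and objectives, the third objective is about detection: "Analysing changes in RR and HR in the context of the system ability to detect a high level of stress". The first two cover feasibility and health outcomes, signal quality, detecting RR and HR, and long-term measurement.

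The Statistical Analysis Plan section contains descriptive statistics, a Pearson correlation of initial RR and/or HR with pre-scan state anxiety, a growth mixture model, and a t-test between the resulting classes. Its one decision standard is: "An Alpha level of 0.05 will be used in all of the statistical tests". It gives no method for deriving the values, no X-1 score that counts as dangerous, and no sensitivity, specificity or AUC. Nor does it mention a hold-out sample, cross-validation, bootstrap correction or second cohort. Study Design leaves open whether RR, HR or both are used, and whether the window is 1 or 2 minutes.

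The Rationale gives the only event rates: "5 to 10% of patients undergoing MRI examinations experience severe claustrophobia or panic attacks during the scanning process", and a further 30% with milder distress.

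**The concern.** A value selected because it separates anxious from calm patients in one data set will usually separate them less well in new patients. The gap grows as cases become fewer and as more signals, windows and cut-offs are tried. Here the same patients supply the values and the evidence that the values work, and the summary moves from there to routine use. Since *positive* is undefined, the reader cannot tell what evidence would be enough.

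The Rationale wants early identification so that staff can act before a patient panics or a scan is wasted. Values that look useful only in the patients who generated them could miss many anxious patients or flag many calm ones.

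**Working it through.** The plan states no power, effect size, accuracy target or success threshold, so there is no figure of its own to reproduce. The checks below are illustrations under stated assumptions.

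**1. Number of cases.** These are the Rationale's rates applied to the maximum enrolment:
- 200 × 0.05 = 10 severe
- 200 × 0.10 = 20 severe
- 200 × 0.30 = 60 with milder distress

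The planned reference is the X-1 score with no stated cut-off, so the real number of cases is unknown. Lower enrolment gives fewer.

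**2. Optimism from choosing and judging a cut-off in the same patients.** Assumptions: normally distributed marker, n = 200, cut-off maximising J = sensitivity + specificity − 1, with 3,000 to 4,000 simulated data sets per setting. For a marker with no information (true J = 0), mean apparent J is:

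| Cases | One signal | Best of two | Best of four |
|---|---|---|---|
| 10 | 0.19 | 0.24 | 0.30 |
| 20 | 0.14 | 0.18 | 0.22 |
| 60 | 0.09 | 0.12 | 0.15 |

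Best of two means RR or HR. Best of four means RR and HR at start and end. Both treat the signals as independent and set them against a single outcome. With start and end readings correlated at 0.8, the best-of-four figures for 10 and 20 cases fall to 0.28 and 0.20.

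For one signal with real but moderate ability (AUC 0.7), apparent against true J is:
- 10 cases: 0.42 − 0.26 = 0.16 overstated
- 20 cases: 0.38 − 0.26 = 0.12 overstated
- 60 cases: 0.34 − 0.27 = 0.07 overstated

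**3. Precision.** An observed sensitivity of 80% has an exact (Clopper-Pearson) 95% CI of 44–97% with 10 cases, 56–94% with 20 and 68–89% with 60.

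**4. What significance shows.** The smallest significant correlation is r = t / √(n − 2 + t²), taking alpha 0.05 as two-sided (the plan does not say):
- n = 200: 1.972 / √(198 + 3.889) = 0.139, so r² = 1.9%
- n = 100: 1.984 / √(98 + 3.938) = 0.197, so r² = 3.9%

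Assume bivariate normality and call the top 10% of X-1 scores cases. Then r = 0.139 corresponds to an AUC of about 0.58 and a sensitivity of about 15.5% at 90% specificity. The positive predictive value is 0.155 × 0.10 / (0.155 × 0.10 + 0.10 × 0.90) = 0.0155 / 0.1055 = 15%, against a base rate of 10%. Taking the top 5% or 30% as cases gives AUCs of about 0.59 and 0.57.

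Steps 2 and 4 are separate illustrations. Step 2 takes its case numbers from cited rates of reactions to MRI, while step 4 defines cases by the X-1 score. They do not describe one scenario.

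**The case against.** The strongest reply is that the plan does not do what the simulation does. It schedules no cut-off optimisation and reports no sensitivity or specificity, so a reader who infers that the study will publish inflated accuracy goes beyond the text. This stands, and it makes the point conditional. It does not remove it, because the summary commits to determining values in these patients and leaves the method open.

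A reader might also infer that p < 0.05 is the rule for adoption. The documents never say so: the SAP sets alpha for its tests, the summary leaves *positive* undefined, and nothing connects the two. The defect is an undefined term, together with the absence of any other statistical standard.

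Next, positive results may refer to feasibility, signal quality or RR/HR monitoring, which are objectives 1 and 2. Routine use as a monitor could follow from those without any anxiety value. This is a fair reading, and the fix must leave room for it. Still, the summary gives anxiety assessment as the main purpose, and the sentence on routine use directly follows the one on dangerous values.

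The sentence is also a summary-level statement of intent in an observational study whose purpose is to determine a possibility. That lowers the stakes, but nothing later in the available text qualifies the sentence.

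Finally, the figures depend on our choices. With 60 cases the optimism is much smaller than with 10. The best-of-four case ignores that start values are paired with pre-scan X-1 and end values with post-scan X-1. It is best read as an upper illustration.

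**Conclusion.** The point holds in a limited form. The plan chooses anxiety-related values in one cohort of at most 200 and links positive results to routine use. In the available text it provides no internal validation, performance measure or confirmation between the two. Performance later reported for those values in the same patients would tend to be too good. For a useless marker the apparent Youden index averages about 0.09 to 0.19 with one signal and up to 0.15 to 0.30 with the best of four, where the truth is 0. These sizes assume a normal marker, a Youden cut-off, 10 to 60 cases and, for the upper range, independent signals tested against one outcome.

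A significant correlation would not fill the gap, since r = 0.14 at n = 200 (0.20 at n = 100) carries little detection ability.

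The documents do not support saying that a system with no detection ability will be declared ready for routine use: no such decision rule is written. Study conduct is not affected. The claim about implementation for anxiety detection should be corrected.

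**What to change.** 1. **Project summary.** Reword the sentence on routine use. RR/HR values related to anxiety are provisional, and their routine use for detecting anxiety depends on confirmation in separate patients. Keep this apart from any conclusion about signal quality or RR/HR monitoring under objectives 1 and 2.

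2. **Statistical Analysis Plan.** Before analysis, fix the X-1 reference definition and the rule for choosing the values. Report sensitivity and specificity with 95% CIs after bootstrap optimism correction, repeating the choice of cut-off and signal in every resample. The bootstrap cannot be run until the definition and the rule exist, so they come first.

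3. **Interpretation.** State that a significant correlation or class difference alone does not support implementation for anxiety detection.

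No extra patients are needed in this study. The cost is some additional analysis, the work of agreeing a reference definition in advance, and a more modest claim. Confirmation in separate patients would be a later study, needed only if use for anxiety detection is pursued.
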